1.0 Introduction

- Evidence shows that although clinical trials are aimed at producing new strategies for reducing cancer morbidity and mortality, participation remains suboptimal for all populations, especially those from racial and ethnic groups [1-3]. Although some interventions have been found to be effective at enhancing participation, few studies have tested tailored communication activities using innovative communication techniques (perceptual mapping) with aims to address barriers and facilitators for patients and facilitate more engaged discussions with their providers in real world settings. We therefore aim to fill that gap by testing a culturally diverse and patient guided mHealth decision tool called **mychoice**, which allows patients to explore their concerns and questions related to clinical trial participation, as well as create a customized and personalized set of questions to enhance patient-provider communication and increase informed decision making. This study employs a mixed-methods approach using both qualitative and quantitative data to evaluate the effectiveness of the **mychoice** intervention for patients and to explore the provider and organizational factors that impact implementation. A randomized controlled trial will be performed with 270 participants in order to determine the acceptability and feasibility of the intervention, as well as its effects on self-efficacy in discussing clinical trial participation with providers, leading to enhanced informed decision-making. Results will also investigate whether the tool has enhanced effects on minority patients, particularly African Americans. A secondary aim of the study is to evaluate the implementation of the intervention in clinical settings. Implementation evaluation will occur using surveys of medical staff whose patients are participating in the study. These surveys will assess institutional facilitators and barriers to study implementation. We will also conduct cognitive de-briefing interviews after the intervention is completed with key stakeholders at the participating institutions, which will inform a larger implementation study in the future.

2.0 Objectives

- The **primary objective** of the study is to assess the effectiveness of the **mychoice** mHealth tool on perceived patient self-efficacy and decisional conflict, and whether these results are enhanced in minority patients.
- The **secondary objective** of the study is to describe the acceptability and feasibility of implementing **mychoice** in oncology services at three leading cancer centers in Philadelphia.
- **Purpose of the study:** **mychoice** was conceptualized and developed with a Fox Chase-Temple NODAL grant, using extensive formative research, including the use of commercial marketing techniques (perceptual mapping and vector modeling) and

patient engagement, and customized to address the significant barriers for African American patients to consider clinical trials. The tool went through user testing and received excellent reviews, and now is ready for an efficacy test. This study represents the next step in personalized clinical trial education research. It completes the **mychoice** communication tool to make it multi-cultural and thus appropriate for all patients, and tests its effectiveness with diverse cancer patients to improve knowledge and preparation to discuss clinical trials within real world settings. We will also explore organizational factors that impact implementation of a technology-based intervention, an innovative aspect that will provide critical understanding on feasibility to ensure scalability in a large medical setting. Results could inform how a tool like **mychoice** could be implemented in a cancer center and enhance communication about clinical trials between patients and doctors.

- **Specific Aims:**

- **AIM 1:** Test the perceived usefulness and effectiveness of **mychoice** to increase patients' self-efficacy and decrease decisional conflict.
 - **AIM 2:** Describe the acceptability and feasibility of implementing **mychoice** in oncology services at three leading cancer centers in Philadelphia by identifying provider and organizational factors influencing its integration in the clinical space.
- The following **hypotheses** are proposed for Specific Aim 1:
 - **H1:** Compared to a non-tailored education aid, **mychoice** will improve self-efficacy in making a decision about participating in clinical trials for all patients as well as a subsample of underrepresented patients (non-white).
 - **H2:** Compared to a non-tailored education aid, **mychoice** will reduce decisional conflict about clinical trial participation for all patients, as well as a subsample of underrepresented patients (non-white).

3.0 Background/Rationale

- **Background:** Evidence shows that ethnic and racial minorities are significantly underrepresented in clinical trials, which are critical to producing new strategies for reducing cancer morbidity and mortality for all populations [4-22]. Recognizing the complexity of barriers to participation in clinical trials, research has focused on potential strategies to enhance participation. Interventions have shown that provider referrals of minority patients, community outreach, acknowledging and addressing issues of trust, flexibility in intervention methods, and population targeted materials are effective [23-26]. Few studies, however, have tested tailored communication activities to address barriers and facilitators for patients using innovative communication techniques in real world settings – meaning ways these

activities can be integrated into the healthcare workflow - or addressed the unique needs of racial and ethnic minorities.

The **mychoice** communication tool begins to prepare patients to participate in a personal and tailored discussion with their provider about clinical trials as a potential treatment option. It is also customized to address the concerns of those least likely to participate, instead of providing a more general look at clinical trials- a common trait of other available tools. Previous research has shown that patient education before the first oncologist visit improves knowledge, attitudes, and preparation for decision making about clinical trials [27] and integrating these tools into the clinical encounter is critical. In addition, using innovative communication techniques (perceptual mapping and vector modeling) to validate and explore salient messages across diverse cancer patients provided new insights into tailoring messages and personalizing patient/provider communication. Insight gained from validation of the intervention will improve the decision making process, and inform a large scale integration of **mychoice** to affect patient perceptions and increase willingness to participate in clinical trials, especially in minority patients.

In addition, we will assess barriers to implementation when introducing the tool in diverse cancer centers, each with different protocols and patient populations, to inform a future proposal. Using the Consolidated Framework for Implementation Science (CFIR), one of the predominant implementation science research frameworks, we will focus on five domains: intervention characteristics, outer settings, inner setting, characteristics of individuals (patients and providers), and process [28]. Implementation science is becoming an important component of intervention implementation and we aim to use this framework to ensure success.

- **Preliminary Data:** To address the issue of clinical trial participation, we developed **mychoice (IRB #14-811)** to target unique barriers of underrepresented populations and prepare them for a discussion about clinical trials with their providers [29-38]. The intervention was developed with stakeholder (both patients and providers) involvement and includes real life stories of cancer patients. The intervention, initially focused on African American cancer patients, was based on mixed-methods formative research including in-depth interviews (Phase I), a survey of African American cancer patients using perceptual mapping and vector modeling to guide the development of the communication messages within the intervention (Phase 2), and message and user testing of the mHealth tool with African American cancer patients who had never participated in clinical trials (Phase 3).

In Phase 1 we conducted in-depth interviews with 16 African American cancer patients. Investigators reviewed and developed themes/subthemes, which resulted in eight themes: knowledge, benefits, disadvantages, social support, decision influencers, provider beliefs, personal history, and value of clinical trials. Results from these interviews were used, along with a thorough literature

review, to inform the development of a quantitative survey that was used in Phase 2.

Phase 2 was completed with 41 African American adult cancer patients, just over half (53.7%) of whom indicated they had never participated in a clinical trial. Surveys occurred either in person or over the phone and participants were asked to report how much they agreed or disagreed on a 0-10 scale (0=strongly disagree, 10=strongly agree) with statements regarding clinical trials' helpfulness, benefits, barriers, value, support from those around them, and beliefs about healthcare providers. T-tests revealed significant perceptual differences between individuals who had participated in a clinical trial and those who had not. Based on the perceptual maps that were generated, the research team developed message strategies to address those issues found to be important in the maps.

[figure not shown]
The resulting *mychoice* mHealth prototype was then developed, working with an app development company and in consultation with our research staff and oncologists. This iterative process included many changes to content, visuals and narrative. In addition, since patient-provider communication and informed decision making was a main theme, we chose to make the mHealth tool interactive to provide patients with an easy way to ask providers questions that were tailored to their interests. The tool combines text, animation, and videos of real patients discussing the identified themes. User testing of the *mychoice* prototype showed that the communication tool was easy to use and understand and was perceived to be very helpful in preparing patients to discuss clinical trials. Feedback from the user testing with predominately African American patients indicated that the patient videos should be more diverse showing a broad representation of races and ethnicities. In addition, a more culturally diverse, rather than a targeted intervention for only African Americans, would be more representative of real world settings. Therefore, the patient videos are being expanded for the current version.

- **Significance:** Participation in clinical trials is a serious and complex decision, and many patients of all races and backgrounds have limited knowledge and understanding of clinical trials as a treatment option. Although much research has been conducted to explore the barriers to participation, there has been a call for more intervention research to address these barriers [39]. A fundamental aspect of patient focused interventions is an exploration of their personal questions and concerns, without which it is difficult for patients to become empowered to participate in an informed or shared decision making process. However, there remains limited empirical research to suggest which messages are most salient to a diverse range of patients to improve decision making, and how decision tools can be tailored to enhance the patient-provider communication dyad. This research will provide insight into that process when the decision is participation in clinical trials.

4.0 Study Design

a) Recruitment methods

- We will recruit a total of 270 patients (~~100-130~~ at FCCC via the medical oncology, radiation oncology, and surgery units and 100 at TUHS via the cancer center). The remaining ~~40-70~~ patients will be recruited at Thomas Jefferson University Hospital and The University of Pennsylvania We anticipate that approximately 20% of the participant pool will be non-white which should provide sufficient number to perform sub-analyses of effects. We will monitor this during recruitment, however, and if we find that we are not reaching this number of non-white participants, we will change the protocol to focus on recruiting only non-white participants.
- There are three ways that patients will be recruited for the study at FCCC. This is shown in Figure 1.

- (1) First, at FCCC, [name] will collaborate with FCCC oncologists to identify patients who might be offered a clinical trial but who have not participated in a clinical trial previously. A patient information card and a flyer have been developed for oncologists to provide to patients (see

Appendices A and B). Oncologists will suggest the study to patients at regular visits and be instructed to either go to the Resource and Education Center at Fox Chase, or find a study representative in the waiting area at a table who is wearing a mychoice pin. Mychoice study staff will be in the waiting areas of participating oncologists on days/times that are busiest. If staff are not available that day, they can go to the REC. If the patient approaches a study staff, they will meet the patient in a designated private space, consent them, and give them the option of doing the study then on either a provided iPad or go to the REC to do the study on a computer.

- (2) Study staff will also be available in the common areas of FCCC at a table. Patients can come up to the table and ask about the study. We will also have a small “wheel” that is a game that patients can play to win small prizes (candy, umbrella, \$5 gift cards). All patients who come up to the table can play and win a small prize; there is no requirement to enroll in the study to play. If they are interested in the study, we will provide an information card and answer any questions they have. They can then complete consent and do the study then (as above) or have the option to complete the study at home.
- (3) Another way for patients to participate is through a referral by REC staff. When patients go to the REC, staff will provide information to the patients about the study. If they are interested, REC staff will go through the above steps to consent a patient and provide them an iPad or computer to complete the study.
- (3) The last way for patients to participate will be by self-referral. Cards and posters will be available throughout the waiting areas. On this card are the study email and phone number. Patients could use these to contact study staff who will explain the study and verbally consent people over the phone and then provide the option to come to do the study at home or at the REC. Because this consent is occurring over the phone, staff will use a script (provided) to explain the study and screen for eligibility. A waiver of document of consent has been provided to assist with this process. After they have verbally been consented for the study, they will be sent a link to the study through the RedCAP system and provided information on how to complete the study. They will be directed to review the study consent and indicate their willingness to participate by entering their name as an e-signature. They then will be asked to do the same with the HIPAA waiver. Once they agree, they will be directed to the baseline survey.
- Patients recruited at TUH, Jefferson, and HUP will follow the same recruitment strategies, but will only be recruited by Physician Referral and Self-Referral. There are no REC staff at these institutions, so recruitment strategies will rely solely on study staff and physicians. Study staff will be in the waiting rooms prepared for any referrals during busy clinic days.

[figure not shown]
- All study materials, including the pre and posttest and the patient education materials, are programmed in REDCap. If completing the study in person, once the patient agrees to be in the study and is set up in the RedCAP system, study staff will explain this process and have them sign in the REDCap system to indicate they agree to participate (script for staff to follow in Appendix C) and to the HIPAA waiver. Study assignment will be random and programmed into the system
- The email link will provide a contact name, phone number, and email should the participant have any questions or concerns. If they choose to come to the REC because they do not want to do the study at home, we will make an appointment with them to meet them at a designated day/time.
- The REDCap link will include pre/post-tests (Appendices D and E) for all patients, and the appropriate patient education materials based on randomization. (**Note:** Baseline surveys take approximately 15 minutes and post-test surveys take approximately 5 minutes, based on testing.) The pre and posttests as well as the consent form will be integrated into the materials through REDCap. All patients will then be contacted by telephone or email one month post consult by the research staff to conduct a follow-up survey (Appendix F – Treatment Arm; Appendix G – Control Arm). In some cases (i.e. at TUH) follow-ups will be done in person when the patient has returned for an appointment.
- The experimental condition will receive the *mychoice* mHealth Tool (Screen shots (<http://mychoice.sandstorm.notss.com>) of the tool are provided in Appendix G.) The entire tool is available at the URL. The control condition will receive the NCI material on clinical trials: Taking Part in Cancer Treatment Research Studies (<https://www.cancer.gov/publications/patient-education/CRS.pdf>). Both will be provided on the device through the RedCAP system. Participants in the experimental condition will receive a pair of ear buds (which they can keep) to listen to audio/video segments and will receive a printed version of the questions they identify as important to them.
- Patient participants will receive a total of \$50 compensation, provided as a \$25 gift card at initial testing and an additional \$25 upon follow-up survey. These will be provided in person if they choose to complete the study in person or via mail if they choose to complete the study at home. Recruiters and physicians interviewed about implementation will not receive compensation.

b) Inclusion and exclusion criteria

- **Eligibility criteria for participation in the RCT are:** 1. 18 years of age or over; 2. Active diagnosis of invasive cancer (any diagnoses); pre or post chemo/radiation/surgery; 3. Able to speak and read English
- **Exclusion:** Participated in a therapeutic trial in the past

c) Procedures involved in the human research

o Study Design: (Figure 2)

The primary outcomes are decision-related self-efficacy and decisional conflict. Secondary measures will include patient-related outcomes such as increased knowledge, use of **mychoice**, increased patient activation, and perceptions of the provider encounter. Table 1 on the following page describes the study measures.

- o **Randomization.** Upon completing the informed consent form, patients will be randomized to either **mychoice** group or control group by RedCAP at a 1:1 ratio. The system will randomly assign participants as they enter into the system after they have been consented to the study.

Table 1. RCT Study Measures

Measure	Source	Description	Pre	Post	1 month follow-up
Demographics	NIH	Age, education, insurance, income, race, ethnicity, gender, living situation (8 items)	X		
Cancer and Clinical Trial Experience (personal and family/friends)		Cancer type, stage (6 items)	X		
Technology Use	HINTS	Mobile, smartphone, computer, tablet (5 items)	X		
Health Literacy	SILS	1 item	X		
Clinical Trial Perceptions	[name], [name]	Test perceptions over time using perceptual mapping – knowledge, benefits, concerns, perceptions/experiences with cancer treatment, beliefs about health care providers and your health (48 items pre; 31 post; 43 follow up)	X		X
Patient Activation (Decisional Engagement Scale)	Hoerger, et al (DES-10)	2- scales decision making preference (1 item), Comfort with interacting with physician (10 items)	X		X
Patient Self-Advocacy Scale	Brashers et al.	Perceptions and self-reported behaviors about information seeking and provider relationship (12 items)	X		
Knowledge of Clinical Trials	Campbell	Knowledge of clinical trials (reduced items; 16)	X	X	X
Self-Efficacy	PEPPI	Confidence in communicating with Physician (10 items)	X	X	X
Decision preparation scale (PrepDM)	Bennett, et al	Value of mychoice in preparation to make a decision (10 items)		X	
Perceived Shared Decision Making (CollaboRATE)	Barr, et al	Patient perceptions of effort to discuss concerns			X
Shared Decision Making	SDM Q-9 Kriston et al	Patient perception of shared decision making with provider (12 items)			X
Decisional conflict	Ottawa	Decision conflict (revised; 13 items)	X	X	X
Clinical Trial Intention	Adapted from Ottawa Patient Decision Aid	If offered, would be considered (1 item)	X	X	X
Satisfaction with patient materials	CISRC adapted	Helpfulness and recommendations of materials (app or standard brochure) (3 items post; 13 items follow-up)		X	X
Experience with clinical trial discussions		Self-reported experience about clinical trial discussions with provider (6 items)			X
Satisfaction with Decision	Enswistle, et al	Satisfaction with decision about clinical trials (6 items)			X

To assess implementation issues and address Specific Aim 2, we will use the Consolidated Framework for Implementation Research (CFIR) to guide the implementation evaluation, focusing on the acceptability and feasibility of implementing the *mychoice* study as well as the integration of this tool in ongoing practice. This evaluation is descriptive in nature. To evaluate the acceptability and feasibility of the proposed *mychoice* study, we will collect data from the initial planning meetings, review of recruitment logs and files, as well as surveys from physicians who have patients that are participating in the study. Meeting notes will be kept and used to design the recruitment process, procedures, and logs. Prior to the start of recruitment (using REDCap; Appendix H) and at project end (will be developed based on how intervention is implemented in sites), an online survey will be conducted with each physician who has patients who are participating in the study. The survey will assess level of commitment to the project and potential barriers. The survey will include key constructs from CFIR, such as perceptions of intervention strength, relative advantage, trialability, patient needs, self-efficacy, and champions. During the recruitment period and throughout the study, recruiters will keep logs of the number of identified patients, number of consented patients, and notes regarding challenges and opportunities in the recruitment process. At the end of the recruitment, the PIs will conduct debriefing interviews with the stakeholders (guide to be developed based on implementation) at each site to more fully explore the challenges and opportunities for ongoing implementation and sustainability (Figure 3). Table 2 describes the measures for the implementation evaluation.

Figure 3. Implementation Process Study Design

[figure not shown]

Table 2. Implementation Constructs

CFIR Constructs	Baseline Survey	End of Study	Debrief Interviews	Meeting Notes
I. Intervention Characteristics				
Source	X	X		
Evidence Strength & Quality	X	X	X	X
Relative Advantage	X	X	X	X
Complexity	X	X	X	X
II. Outer Setting				
Needs & Resources of Those Served by the Organization	X	X	X	X
III. Inner Setting				
Culture	X	X		
Implementation Climate	X	X	X	X
Tension for Change	X	X		
Readiness for Implementation	X	X		
Leadership Engagement	X	X		
Available Resources	X	X		
IV. Characteristics of Individuals				
Knowledge & Beliefs about the Innovation	X	X	X	X
Self-Efficacy	X	X	X	X
V. Process				
Planning			X	X
Engaging			X	X
Formally Appointed Internal Implementation Leaders			X	X
Champions			X	X
Key Stakeholders			X	X
Executing			X	X
Reflecting & Evaluating			X	X

- **Timeline: This is a 33 month project (4/2017-12/2019)**

		12/17	6/18	7/19	12/19
Months:	1-6	1-9	10-15	16-28	29-33
Revisions based on initial user testing	X	X			
Review by key stakeholders	X	X			
New patient testimonials to increase diversity	X				
Final Production	X	X			
Create Study Instruments		X			
Finalize data management system		X	X		
Recruitment process established at sites					
1. Fox Chase			X		
2. Temple			X		
3. Jefferson				X	
4. Penn				X	
IRB review and approval at study sites					
1. Fox Chase			X		
2. Temple			X		
3. Jefferson				X	
4. Penn				X	
Recruit 270 Patients				X	
Conduct pre-intervention implementation surveys with participating staff				X	
Conduct baseline, intervention, and post test				X	
Conduct one-month follow-up surveys				X	
Conduct post intervention implementation surveys				X	
Data Analysis – Patient Surveys					X
Tracking analysis-metrics in mychoice					X

In-depth implementation interviews with site stakeholders					X
---	--	--	--	--	---

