19.0 Appendices

- A: Patient Card
- B: Flyer
- C. Script for electronic informed consent
- D: Baseline Survey
- E: Post Test Survey
- F: Follow-up Survey – Treatment Arm
- G: Follow-up Survey – Control Arm
- H: Physician Survey – Pre Intervention

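### Staff who conduct the 1-month survey by telephone or in person use forms labelled by arm, so they can be inferred to know the allocation while asking the subjective primary scales; no masking is described and survey mode is left open

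*Combined protocol and SAP*

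**What the plan says.** - **Who collects the data, and how.** Section 4.0, a) Recruitment methods: "All patients will then be contacted by telephone or email one month post consult by the research staff to conduct a follow-up survey". The next sentence adds a third mode: "In some cases (i.e. at TUH) follow-ups will be done in person when the patient has returned for an appointment".
- **The forms.** The same paragraph gives a separate form for each arm; patients are contacted "by the research staff to conduct a follow-up survey (Appendix F – Treatment Arm; Appendix G – Control Arm"). The list in Section 19.0 confirms it: "F: Follow-up Survey – Treatment Arm" and "G: Follow-up Survey – Control Arm". The baseline and post-test surveys (Appendices D and E) are each a single form for all patients, delivered in REDCap.
- **What is measured.** Section 4.0, c): "The primary outcomes are decision-related self-efficacy and decisional conflict". Table 1 gives self-efficacy as 10 PEPPI items and decisional conflict as 13 revised Ottawa items. Each has one definition for both arms and is marked at pre, post and 1 month. The satisfaction row is the one that refers to the two materials: "Helpfulness and recommendations of materials (app or standard brochure) (3 items post; 13 items follow-up").
- **Which time point counts.** Section 13.0, H1 Analysis, names the 1-month follow-up as the principal endpoint.
- **What is absent.** No section describes masking of patients, follow-up staff or analysts. No section says what share of patients will be surveyed by each mode, or whether an email contact leads to a self-completed survey. Section 13.0 does not mention mode.

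**The concern.** Self-efficacy and decisional conflict are opinions that a patient gives about himself or herself. Asked aloud, they can be moved by tone, prompting or the wish to please. If the person asking knows which material the patient received, any such movement can differ between arms. Randomisation balances patients at entry; it does not protect against a difference that arises when the outcome is measured. Nor does a larger sample help, because the shift stays while the standard error shrinks.

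The arm-specific forms appear only at the visit that carries the principal endpoint. The most natural direction of bias is in favour of mychoice, since the staff who follow patients up belong to the team studying it. That direction is an inference and not something the documents state.

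**Working it through.** **1. Does the text put the allocation in front of the person asking?**

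- Staff conduct the 1-month survey (Section 4.0).
- The survey is a different form for each arm, named by arm (Sections 4.0 and 19.0).
- The primary scales are due at that contact (Table 1), and no other 1-month patient form is listed.

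For a telephone or in-person survey, it follows that staff have an arm-named form open while asking the primary questions. This is a strong inference from the form names, not a sentence in the protocol. For email contact it does not follow, because patients may complete the form themselves.

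**2. Are arm-specific forms needed for the primary scales?** Nothing in Table 1 suggests so: each scale has one definition for both arms. The post-test also carries satisfaction items on the materials, and only one post-test form is listed for all patients.

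**3. The plan's own sample size.** Inputs from Section 13.0, Power: effect 0.47 SD, two-sided alpha 0.025, power 80%. The two-sample t-test gives 87.3, rounded up to 88 per group. With 20% dropout, 2 × 88 / (1 − 0.20) = 176 / 0.80 = 220. Both stated figures reproduce, and power at 88 per group is 80.3%. There is no arithmetic error here to correct.

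**4. Illustration of what a reporting shift would do.** Assumptions that are not in the documents:

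- There is no true effect.
- A shift of b SD favours mychoice among a share s of patients, so the average shift is δ = b × s.
- There are m = 108 analysed patients per arm, from 270 × 0.80 / 2.
- The test is a plain two-sample t-test on each outcome at the Power paragraph's 0.025.

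The rejection probability is P(|T| > t_c), where T is noncentral t with 2m − 2 = 214 degrees of freedom and noncentrality δ × √(m/2) = δ × √54, and t_c = 2.257. For b = 0.10 and s = 100%, the noncentrality is 0.10 × 7.35 = 0.735 and the probability is 6.7%.

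| Assumed shift b | all affected | half affected | a quarter affected |
|---|---|---|---|
| 0.05 SD | 3.5% | 2.7% | 2.6% |
| 0.10 SD | 6.7% | 3.5% | 2.7% |
| 0.15 SD | 12.6% | 4.8% | about 3% |

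The nominal value is 2.5%. With 88 per arm and all patients affected, shifts of 0.05 and 0.10 SD give 3.3% and 5.9%. The estimate moves by δ itself: an average shift of 0.10 SD is 0.10 / 0.47 = 21% of the effect the trial is sized to detect.

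**5. How many patients could be affected?** The documents do not say. Temple, the site named for in-person follow-up, is to recruit 100 of 270 (37%), but only some of its follow-ups are in person. The telephone share at any site is not given.

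**The case against.** The strongest reply has five parts.

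- **Email is a stated mode.** Section 7.0 has all survey data gathered in REDCap, and Section 4.0 describes sending patients a link to take part remotely. If email contact means self-completion, no one asks those patients anything. This stands. A reader might infer that all 1-month primary data are taken by staff who know the arm; the documents do not support that.
- **Appendices F and G are not available to this review.** A reader might infer that the primary scales follow, or are mixed with, the items on the materials. That cannot be known: the scales may already come first and be worded identically. This stands as a limit on the claim. It does not help with the labels, which show the arm whatever the order.
- **Forms are not the only route to unblinding.** Section 4.0 gives mychoice patients ear buds and a printout of their chosen questions, so staff who ran an in-person session may know the arm anyway. This also stands: changing the forms is a partial remedy.
- **Patients know what they used.** Courtesy towards the study team needs neither labelled forms nor informed staff. That bias is separate, and masking the caller would not remove it.
- **The post-test is a partial check.** Both scales are also taken immediately after the education, on a single form, and Section 13.0 includes both time points with a time-by-group interaction. This allows a comparison but does not protect the 1-month result, since a real change over the month and a change in how the data were collected would look alike.

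**Conclusion.** The point holds for patients surveyed by telephone or in person. For them the plan, followed as written, shows the allocation to the person asking subjective primary questions at the principal endpoint. It describes no masking and gives the analysis no way to see the effect of mode.

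The size is unknown. Under the assumed shifts, per-outcome error lies between about 2.6% and 12.6% against a nominal 2.5%, depending mostly on how many patients staff interview. The upper figures need every patient to be affected, so they are a worst case and not an expectation. The calculation also simplifies the planned analysis: it omits the baseline-adjusted mixed model and the Benjamini-Hochberg adjustment.

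A reader might go further and conclude that the trial's primary result would be invalid. The documents do not support that. They show an avoidable exposure whose extent they leave open. The change below is a cheap improvement that should be made, not a condition for the trial to be interpretable.

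**What to change.** - Replace the two follow-up forms with one REDCap block that is identical in both arms and carries no arm label. Put self-efficacy and decisional conflict at the start.
- Put the items specific to mychoice or the brochure on a separate page that opens only after the common block is locked.
- Where existing staffing allows, have the call or visit made by someone who did not run that patient's session.
- Record the mode (telephone, in person or self-completed) for every follow-up. Add to Section 13.0 a sensitivity analysis of the 1-month effect by mode.
- State in the protocol who is and is not masked.

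Self-completion by link may be offered but need not be the default: Section 8.0 puts the survey at about 30 minutes, and relying on self-completion could raise non-response at the principal endpoint.

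The cost is minor rebuilding of two forms and one extra field. What remains is the reporting bias of patients who know their material, and any knowledge of the arm that staff carry over from the session.
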